The target population for this study is all undergraduate students at UVM living off-campus in an independent housing arrangement where they have access to a kitchen. As most junior and senior students live off campus, we expect to recruit mostly junior and senior students. In Spring 2017 there were 2,232 juniors and 2,926 seniors enrolled at UVM, indicating that over 5,000 students could be eligible for the study. For the first two years at UVM, the majority of students live in dorms on campus and are required to have meal plans. The majority of juniors and seniors at UVM then move off campus. This time frame may encompass the first time that many students have had to consider buying and cooking food for themselves. Addressing cooking behaviors during this transition may help establish lifelong cooking habits. Participants will need to have access to a kitchen because the study examines how to influence and increase cooking behaviors. Participants may have roommates with whom they share a kitchen, however they will not be eligible if they live with parents or guardians, as in this scenario they likely have less required independence around cooking. Participants who already cook dinner at home four times per week or more will not be included in the study, as they are already cooking at home frequently and do not need to be motivated to do so. Previous research has indicated that the majority of college students do not prepare dinner even weekly, so we do not anticipate this inclusion criteria greatly restricting our sample.¹⁴

Inclusion criteria:

- Student at the University of Vermont
- Age 18-25
- Cooks dinner at home no more than 3x/week
- Access to a kitchen at home
- Lives independently (may have roommates but may not live with guardians)
- Availability during scheduled cooking classes/demonstrations

Phase 1: The Cooking Program

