Following signed consent participants will be asked to complete a few baseline tasks to be fully eligible for participation in the study. These tasks include three days of food tracking using ASA-24, baseline surveys, submission of cooking frequency and food photos, and finally a one-on-one interview with study staff to discuss their participation. These baseline tasks are intended to ensure participant compliance and retention during the 18-week intervention.

Eligible participants will be assigned to one of four scheduled class periods based on their stated availability or recruited for the control condition. Once all classes are full, a random assignment table will be used to determine the group assignment for each class period. Participants will then be informed of their group assignment (active with follow up or active no follow up). Participants who are in the control condition will be randomly assigned to either a group that receives follow-ups or a group that does not. Groups will not be stratified by any criteria, and instead will be determined based upon participant availability.

Surveys will be administered through the study REDCap website at baseline and study end. Participants will receive links to the questionnaires and reminders to complete questionnaires via email. These measures are outlined in greater detail below. In addition to questionnaires, weekly data collection (Photo Elicitation and Cooking Frequency) will be administered through REDCap. Participants will receive a weekly email with links to a REDCap data collection tool. Participants will receive reminders to complete weekly data submissions, and will be given information regarding a helpline for using the study website and data entry.

Table 1 outlines when each measure will occur during the study.

Measures	Baseline	Weekly	Phase 1	Phase 2	Phase 3
ASA24					
HEI (calculated)					
CAFPAS					
Cooking Perceptions and Behaviors					
PSS					
Intuitive Eating Scale					
Interoceptive Awareness					
Cooking Frequency					
Photo Elicitation					
Class Evaluation					
Meal Kit Evaluation				X	
COVID-19 Questionnaire					X

Quantitative Measures

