the conclusion of the study, investigators will randomly select five participants from each group to interview about their photos. The interviews will ask questions about why the photos represented healthy or unhealthy meals to the participants, where the meals were prepared, how the photos may have changed over time, and how the various interventions may have affected the photos.

Cooking Class Evaluation – At the conclusion of the cooking classes for the intervention group there will be a class evaluation given to assess participants’ impressions of the classes or demonstrations. This evaluation will be available on the study website, and participants will have time in class to complete the evaluation and can do so on their smart phone or tablet. Participants will also have the option to complete this evaluation at a later time on their home computer.

Meal Kit Evaluation – At the conclusion of the Meal Kits (Phase 2) participants in Groups A and C (those receiving the meal kit intervention) there will be an evaluation given to assess participants’ impressions of the meal kits they received. The evaluation will be included in the emailed set of surveys for participants in Groups A and C.

Intervention

Phase 1 will be in October of 2019. Participants in all active cooking groups will attend a weekly 2-hour cooking class to learn how to prepare the same meals. Participants will sample the meal at the end of class and the chef will walk them through a sensory exercise. At the end of each class, participants will be provided with the recipe for the next class and asked to create a timeline for the various steps of preparation. Participants will bring this timeline to class and discuss as a group before preparing the meal or watching the demonstration.

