After the final cooking class, participants in groups B and D will receive no further instruction, though they will be asked to complete surveys and data collection through the remainder of the study phases. Phase 2 will begin in mid-January 2020. Participants in Groups A and C will receive weekly meal kit deliveries for 6 weeks. Meal kits will be delivered to students’ homes once per week and will include the ingredients and instructions for preparing 3 separate meals. Phase 3 will be immediately following phase 2. Participants in groups A and C will receive an email at the beginning of each week for the next six weeks that provides them with 5 healthy recipes developed by the study team. Students will generally receive the same recipes though; modifications may be made for participants with special dietary restrictions.

Facilities and Equipment Needed

Cooking Labs – The cooking classes and demonstrations will take place in the Nutrition and Food Sciences teaching kitchen located in the Marsh Life Science building. The teaching kitchen has room for 16 students to complete hands on cooking labs, and an additional space where students can get directions, eat, and watch cooking demos. The kitchens are fully stocked with the necessary kitchen equipment.

Follow-up Data Collection

Participants will be alerted by email to complete their follow-up assessment questionnaires which are anticipated to take approximately 30 minutes to complete and 3 days of the ASA24 (approximately 30 minutes per day).

All participants will be offered small incentives such as cooking equipment, cookbooks, gift cards, etc. (valued at approximately \$ 5-25) after completion of the follow-up data collection. Those in the Control Group will also receive a small incentive for completing their baseline measures.

For research involving survey, questionnaires, etc.: Describe the setting and the mode of administering the instrument and the provisions for maintaining privacy and confidentiality. Include the duration, intervals of administration, and overall length of participation. (describe and attach all instruments)

Not applicable

Questionnaires and ASA-24 logs will be administered at baseline and at the end of each study phase.

Photo elicitations and cooking frequency surveys will be administered weekly during the active study phases.

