2. for the route of administration specified? If no, provide justification for route and describe the method to accomplish.

3. for the intended action?

Device (s)

Not applicable

Device name and indications (attach investigational device brochure)

Is it FDA approved: (include FDA IDE Number)

1. for indication specified? If no, provide justification for proposed use and source of the device.

Risk assessment (non-significant/significant risk) - PI or sponsor needs to assess risk of a device based upon the use of the device with human subjects in a research environment.

SUBJECT CHARACTERISTICS, IDENTIFICATION AND RECRUITMENT

Subject Selection: Provide rationale for subject selection in terms of the scientific objectives and proposed study design.

This study aims to evaluate changes in food agency including cooking frequency between the two interventions. Therefore, subjects are selected to provide a sample of individuals positioned to increase their food agency and cooking frequency. Towards this end, only individuals who are cooking (from scratch) no more than 3 meals at home per week will be eligible. Additionally, all participants must have daily access to a kitchen with basic appliances and equipment (stove, oven, refrigerator, sink).

All participants must have weekly access to a computer or smart device with internet access in order to report photo elicitations and cooking frequencies. The study does not seek to introduce use of this technology to naïve users who have no daily access. Furthermore, potential participants will be required to demonstrate some ability to comply with study intervention procedures to be eligible. Specifically, they must complete an online dietary self-monitoring diary for 3 days, photo elicitations, and cooking frequency surveys so that only adequately motivated individuals who are likely to stay engaged for the full 18-week study period are enrolled and randomized.

Vulnerable Populations: Explain the rationale for involvement of special classes of subjects, if any. Discuss what procedures or practices will be used in the protocol to minimize their susceptibility to undue influences and unnecessary risk (physical, psychological, etc.).

Not applicable

Number of Subjects: What is the anticipated number of subjects to be enrolled at UVM/UVM Medical Center and in the case of a multi-center study, with UVM/UVM Medical Center as the lead, the total number of subjects for the entire study.

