This is a pilot study with no previous data available to calculate expected statistical power. The sample size chosen was practical as our foods lab can only accommodate 16 people at a time. One group of each intervention arm (four) would give us data on approximately 64 subjects. This preliminary data will be used to determine the sample size power needed for a larger study with sufficient statistical power.

Inclusion/Exclusion Criteria: Eligibility and ineligibility criteria should be specific. Describe how eligibility will be determined and by whom. Changes to the eligibility criteria at a later phase of the research have the potential to invalidate the research.

Interested individuals will be directed to a study application that provides details about the study program and asks a series of screening questions. These questions are intended to determine basic eligibility for the study. Ineligible applicants will be notified of their ineligibility and directed to other campus resources related to cooking and meal planning. Eligible applicants will be directed to sign up for an in-person information session.

Inclusion criteria:

- Student at the University of Vermont
- Age 18-25
- Cooks dinner at home no more than 3x/week
- Access to a kitchen at home
- Lives independently off campus (may have roommates but may not live with guardians)
- Availability during scheduled cooking classes/demonstrations

Individuals will be excluded from the study if they do not complete baseline data collection measures prior to the first class meeting. Baseline data measures include four questionnaires (PSS, CAFPAS, Cooking Behavior, and intuitive eating scale), three days of ASA-24 logs, one photo elicitation survey, and one cooking frequency survey.

Inclusion of Minorities and Women: Describe efforts to include minorities and women. If either minorities or women are excluded, include a justification for the exclusion.

Women and minorities will be included. During recruitment, we will work with UVM Office of Student and Community Relations to ensure that our recruitment materials and procedures capture eligible students of all demographics.

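### Neither eligibility list screens for spring presence, when kits are delivered to homes, and the class arms appear to learn their support allocation before Phase 1

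*Combined protocol and SAP*

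**What the plan says.** **Eligibility.** The lists under Study Population and under Inclusion/Exclusion Criteria cover student status, age, limited dinner cooking, a home kitchen, independent living and "Availability during scheduled cooking classes/demonstrations". The second list words the housing item as "Lives independently off campus (may have roommates but may not live with guardians". The housing, kitchen and student-status items carry no date. Neither list mentions the spring term.

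**Timing.** The Intervention section states "Phase 1 will be in October of 2019" and "Phase 2 will begin in mid-January 2020". It continues: "Participants in Groups A and C will receive weekly meal kit deliveries for 6 weeks". Kits go to students' homes. Then "Phase 3 will be immediately following phase 2", with recipes sent by email for six weeks.

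**Allocation.** Under Procedures, class periods are filled by availability. Once they are full, a random table assigns each class period, and "Participants will then be informed of their group assignment (active with follow up or active no follow up"). Control participants are randomised separately to follow-up or none, at a time that is not given.

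**Retention.** Procedures requires baseline tasks and an individual interview, aimed at compliance and retention. Subject Selection says the tasks serve so that only motivated people "likely to stay engaged for the full 18-week study period are enrolled and randomized". Withdrawal Procedures allows the investigator to withdraw someone who moves more than 120 miles away and does not plan to return during the intervention phases.

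**The concern.** Support versus no support is the contrast behind Aim 2. As operated, it is also the only contrast with a random draw: class places follow availability, and controls are recruited afterwards from applicants who went no further (Consent Procedures, Control Condition). The draw acts only in spring, but nothing in the eligibility lists looks at spring. Study Population expects mostly juniors and seniors. One who finishes in December, leaves for the spring term, or moves back with parents can meet every listed item at screening.

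Three consequences follow.

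- Students allocated to kits may be unable to receive them, or may cook in a household of the kind that the protocol excludes because it calls for less independence around cooking. Kept as allocated, they dilute the contrast. If they stop responding, they are lost from it. Statistical Considerations plans repeated measures ANOVA for Aim 2 and states no rule for missing data or non-receipt.
- Class participants told in the fall that they will get nothing further have weeks to disengage before support begins, so loss can differ between A and B.
- Those told that free kits are coming may behave differently during Phase 1, which would reach the Phase 1 measurements.

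**Working it through.** **1. The plan's own figures reproduce.** Sample size: 4 × 16 = 64. Intervention weeks: 6 + 6 + 6 = 18.

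**2. Calendar.** Inputs: Phase 1 starts between 1 and 31 October 2019 (six weeks do not fit inside October, so the month is read as the start); mid-January is taken as 15 January 2020, or 13 to 20 January for the end dates; each phase lasts six weeks.

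- End of classes: 1 October + 42 days = 12 November; 31 October + 42 days = 12 December.
- First class to first kit: 106 days = 15.1 weeks, or 76 days = 10.9 weeks.
- Gap from last class to first kit: 15.1 − 6 = 9.1 weeks, or 10.9 − 6 = 4.9 weeks.
- Kits end 24 February to 2 March; recipes end 6 to 13 April 2020.
- Calendar span: 15.1 + 12 = 27.1 weeks, or 10.9 + 12 = 22.9 weeks, of which 18 are intervention weeks.

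A class-arm student told of A or B before the first class would thus know the allocation 11 to 15 weeks before support starts.

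**3. Does any existing step screen for spring presence before allocation?**

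- Inclusion lists: no. Only class attendance is tied to a schedule, and Groups C and D attend no classes.
- Baseline tasks and interview: these test compliance and discuss participation. Spring presence is not named. For controls, the Consent Procedures text describes only a consent appointment and online baseline measures.
- Engagement intent: this concerns motivation. A motivated student can still leave.
- 120-mile rule: discretionary, applied after enrolment, and it would remove people already allocated. It does not reach a student who moves in with parents nearby.

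**4. Illustrative size.** The documents give no share of students away in spring. For an assumed share f, the expected number affected is 64f (16f per group), and the chance of at least one among the 32 allocated to support, if students leave independently, is 1 − (1 − f)^32.

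- f = 5%: 3.2 of 64 (0.8 per group); 81%.
- f = 10%: 6.4 of 64 (1.6 per group); 97%.
- f = 20%: 12.8 of 64 (3.2 per group); 99.9%.

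If affected A and C students stay in the analysis and gain nothing from kits, the average kit effect is multiplied by 1 − f: 0.95, 0.90 or 0.80. This applies to Phase 2 only, because recipes can still arrive by email.

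**5. Why no standard-error figure is given.** With 64 independently allocated participants, losing a share f would multiply the standard error by 1/√(1 − f). That does not describe A versus B, which is allocated by class period. A class-period mean with m students and within-class correlation ρ has variance proportional to ρ + (1 − ρ)/m. Only the second term grows as m falls, so for ρ > 0 the inflation is smaller than the simple formula gives. The documents supply no ρ. Power figures that treat students as independent fail for the same reason.

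**The case against.** The strongest defence is that the protocol did think about retention. It has a run-in, an individual interview and a relocation rule, and applicants are told of their responsibilities beforehand. Staff may well learn at interview that a student is leaving. This is also a pilot sized by lab capacity, and the Phase 1 comparison does not depend on spring residence. All of that stands. It makes the problem smaller and less certain, but none of these steps asks the question before allocation.

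A reader might infer several stronger things that the documents do not support:

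- *That eligibility is limited to fall.* Only class availability is tied to a schedule. The housing and kitchen items are undated, so they are silent about spring.
- *That absent students cannot receive support at all.* Recipes, which fill six of the 12 support weeks, go by email. Kit delivery is not stated to be limited to the campus area. What is at risk is receipt of kits and use in independent housing.
- *That a known fraction or a known loss of precision follows.* No share is given, and nothing shows that any enrolled student would be away.
- *That 18 weeks is an error.* It is correct for intervention weeks. Only the term study period in Subject Selection is loose, and no calculation depends on it.

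Announcement before Phase 1 is also an inference. Procedures gives the order (classes full, draw, announcement) but no date.

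**Conclusion.** The point holds as a gap in design that is cheap to close. Followed as written, the plan can allocate students to spring support without having asked whether they will be there, and it appears to tell the class arms their allocation well before support begins. The consequences fall on Aim 2 and the spring part of Aim 3, through dilution or loss, and on Phase 1 only through anticipation. The direction is clear for dilution: towards no difference if affected students are kept. Differential loss and anticipation could act either way.

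The size is unknown. The 5% to 20% range is an assumption for illustration. The dilution factors further assume no kit benefit in affected students and concern Phase 2 alone. The early-announcement part rests on reading the Procedures order as preceding the first class, and it cannot be extended to C versus D because that draw is undated.

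**What to change.** 1. Add to both inclusion lists: *Expects to be enrolled, living independently with kitchen access and able to receive deliveries from January through April 2020.*
2. In Procedures, make and announce the A/B draw (by class period) and the C/D draw only after the end-of-Phase-1 assessment, once the criterion has been re-confirmed. Students who no longer meet it stay in the Phase 1 comparison but do not enter the support draw. Because that decision precedes the draw, it cannot depend on allocation.
3. State in Statistical Considerations that participants are analysed as allocated.

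**Cost.** One screening question, one re-confirmation, wording in three sections, and a short lead time for kit orders, for which the gap of about 5 to 9 weeks after the last class leaves room. Departing students become ineligible, so the sample is slightly narrower. No stated figure changes: the target stays 64 and the intervention 18 weeks.

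The document carries an approval stamp of 14 April 2020, after the dates worked out above. Where allocation has already been made, the usable part is to report spring housing and kit receipt by group, analyse as allocated, and carry items 1 and 2 into the larger study that this pilot is meant to inform.

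Optionally, Subject Selection could say 18 intervention weeks over about 23 to 27 calendar weeks. That is wording only.

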A repeated measures ANOVA analysis will be used to compare changes in intuitive eating, diet quality and food agency over time both within the groups and between the groups. A generalized linear mixed model design will be used to compare the frequency of cooking at home each week over time and between the groups.

Aim 2: To evaluate if providing students with six weeks of a meal delivery service and then six weeks of recipes after completion of cooking classes maintains gains in diet quality, cooking frequency, intuitive eating, and food agency.

Hypothesis 2a: Meal delivery service will better maintain cooking frequency, intuitive eating skills, food agency and diet quality versus recipe provision only. Both meal delivery service and recipe provision will result in more frequent cooking, higher food agency, and higher diet quality the provision of no cooking support.

Hypothesis 2b: During both meal delivery service provision and recipe provision, those in the Cooking Class Condition will maintain higher levels of food agency, cooking frequency, and diet quality than those in the Control Condition.

Repeated measures ANOVA analyses will be used to compare between subjects effects from the meal delivery and recipe only interventions, as well as to compare the material support interventions against the control group. Repeated measures ANOVA will also be used to compare within subjects effects from end of fall semester to the end of each six-week material support intervention.

Aim 3: To positively influence participants' stress levels.

Hypothesis 3: Participants receiving cooking support will have lower scores on a measure of perceived stress than participants who do not receive cooking support. This will be true at all measurement time points.

A repeated measures ANOVA will be used to determine differences both between groups and over time in scores of perceived stress.

Aim 4: To explore the reasons why students cook or do not cook.

Hypothesis 4: There will be common themes defining why student choose to cook or not cook at home.

This is an exploratory aim, and qualitative analysis will be used to deduce popular themes.

Sample Size

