This is a pilot study with no previous data available to calculate expected statistical power. The sample size chosen was practical as our foods lab can only accommodate 16 people at a time. Two intervention groups and two control groups for each study phase will provide data on approximately 64 subjects. This preliminary data will be used to determine the sample size power needed for a larger study with sufficient statistical power.

Risks/Benefits: *Describe any potential or known risks. This includes physical, psychological, social, legal or other risks. Estimate the probability that given risk may occur, its severity and potential reversibility. If the study involves a placebo or washout period, the risks related to these must be addressed in both the protocol and consent. Describe the planned procedures for protecting against or minimizing potential risks and assess their likely effectiveness. Where appropriate, discuss plans for ensuring necessary medical or professional intervention in the event of adverse effects to the subjects. Discuss the potential benefits of the research to the subjects and others. Discuss why the risks to the subjects are reasonable in relation to the anticipated benefits to subjects and others. Discuss the importance of the knowledge gained or to be gained as a result of the proposed research and why the risks are reasonable in relation to the knowledge that reasonably may result. If there are no benefits state so.*

Potential Risks. No social, legal or other risks are anticipated as part of this project. All assessment procedures and intervention recommendations have been used in previous studies without adverse outcomes. Assessment methods reflect measures that have been implemented in numerous studies without difficulties (e.g., dietary intake and cooking behavior questionnaires).

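### Follow-up support (A versus B) is allocated to whole class periods filled by availability, but the analysis has no class term and treats students as independent

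*Combined protocol and SAP*

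**What the plan says.** The Procedures section describes allocation in the class arms in three steps.

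- Filling the classes: "Eligible participants will be assigned to one of four scheduled class periods based on their stated availability or recruited for the control condition".
- Allocation: "Once all classes are full, a random assignment table will be used to determine the group assignment for each class period".
- Disclosure: "Participants will then be informed of their group assignment (active with follow up or active no follow up").

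The section adds that there is no stratification. Controls are handled differently: they are randomised individually to follow-up or none (Procedures; Consent Procedures, Control Condition). The opening summary and Study Design nevertheless describe the trial as randomising 64 students.

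For Aim 2, Statistical Considerations says "Repeated measures ANOVA analyses will be used to compare between subjects effects from the meal delivery and recipe only interventions", and that the same method will "compare within subjects effects from end of fall semester to the end of each six-week material support intervention". For weekly cooking, under Aim 1: "A generalized linear mixed model design will be used to compare the frequency of cooking at home each week". Group and time are the only factors named. No class effect, ICC, design effect or cluster-robust variance appears anywhere.

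Under Sample Size: "Two intervention groups and two control groups for each study phase will provide data on approximately 64 subjects". The figure is set by a 16-seat lab. The section continues: "This preliminary data will be used to determine the sample size power needed for a larger study with sufficient statistical power".

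**The concern.** Classmates are likely to resemble one another. They share a timetable slot that they could attend, the same chef-led sessions, cooking in pairs and group discussion. When support is given to a whole class, any difference between classes becomes part of the A-versus-B difference. An analysis with students as the independent units does not count that variation.

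A versus B is the only comparison of support with no support among students who took the classes, which is what the maintenance question in Aim 2 needs. C versus D is individually randomised, but it concerns students who had no classes, so it cannot show whether support preserves class gains. Reading A versus B as individually randomised would give intervals that are too narrow, and the pilot is meant to feed the planning of a larger trial.

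A secondary point is timing. The order of steps (classes filled, table drawn, students told) suggests that students learn their follow-up group before Phase 1, although no date is given. If so, knowing that meal kits are coming could affect Phase 1 behaviour and the end-of-fall values from which maintenance is measured.

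**Working it through.** **Inputs from the documents.** Four groups of 16 (opening summary); 4 × 16 = 64, which matches the stated total. Lab capacity is 16 (Facilities and Equipment Needed; Sample Size). No alpha, SD, effect size or ICC is given.

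**Assumptions.** Two-sided alpha 0.05; ICC 0.02, 0.05 or 0.10; total SD 1.

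**Classes per arm.** The text supports two readings for the 32 class students:
- 32 / 16 seats = 2 full classes, so one class of 16 per arm.
- 32 / 4 scheduled periods = 8, so two classes of 8 per arm.

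**Design effect,** 1 + (m − 1) × ICC, at ICC 0.05:
- m = 16: 1 + 15 × 0.05 = 1.75; effective n per arm 16 / 1.75 = 9.1.
- m = 8: 1 + 7 × 0.05 = 1.35; effective n per arm 16 / 1.35 = 11.9.

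**Type I error, one class per arm.** The student-level t statistic (30 df) is inflated by √[(1 + 15 × ICC) / (1 − ICC)]. The true error is therefore P(|t₃₀| > 2.042 × √[(1 − ICC) / (1 + 15 × ICC)]). At ICC 0.05: 2.042 × √(0.95 / 1.75) = 1.505, giving 14.3%. At 0.02 the cut-off is 1.773 (8.6%), and at 0.10 it is 1.225 (23.0%). Simulation agrees.

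**All scenarios** (two-class and pooled figures by simulation, 100,000 to 200,000 replicates each):

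| Contrast at one time point | ICC 0.02 | ICC 0.05 | ICC 0.10 |
|---|---|---|---|
| A v B, one class of 16 per arm | 8.6% | 14.3% | 23.0% |
| A v B, two classes of 8 per arm | 6.6% | 9.4% | 13.9% |
| A+C v B+D, one class of 16 | 6.7% | 9.6% | 14.1% |
| A+C v B+D, two classes of 8 | 5.9% | 7.0% | 9.1% |

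At ICC 0 the A-versus-B rate is 5%, as it should be.

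**Change since the end of fall.** A class difference that is constant over time cancels, and the error is 5.0%. If class effects correlate 0.8 over time (student residuals 0.5, both assumed) at ICC 0.05:
- class variance of change: 2 × 0.05 × (1 − 0.8) = 0.02
- student variance of change: 2 × 0.95 × (1 − 0.5) = 0.95
- ICC of change: 0.02 / 0.97 = 0.021

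The error is then 8.8% (one class) or 6.7% (two).

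**Weekly counts.** A rough stand-in for a student-level mixed model used Poisson counts with mean 2 per week for 6 weeks, between-student log SD 0.5, and a t-test on log totals. At ICC 0.02 / 0.05 / 0.10 it gives 7.5 / 11.6 / 18.5% (one class) and 6.1 / 8.0 / 11.0% (two).

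**What a valid test could detect.** With two classes per arm, a class-level test has 2 df and critical t 4.30, against 2.04 on 30 df. At ICC 0.05 the standard error is √(2/16 × 1.35) = 0.411 SD, and 80% power needs a difference of 2.32 SD. The naive test appears to need 1.02 SD. Randomising individuals within class needs 1.02 × √0.95 = 1.00 SD. Splitting four periods two and two gives 6 possible allocations, so the smallest two-sided randomisation p-value is 2/6 = 0.33. With one class per arm there is nothing to compute.

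**The case against.** The strongest reply is that the largest figures belong to a single-time-point test of A versus B, whereas the plan also compares change from the end of fall and support pooled over class and control arms. For change, a stable class effect does no harm. Classes end before Phase 2, so new divergence between classes in spring is assumed rather than shown. That stands, and it is why change should be the focus. It does not remove the problem: Aim 2 also plans between-subjects effects, and Hypothesis 3 is about stress levels at every time point.

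The two-class reading can be disputed. Procedures says the classes will be full, and four full classes of 16 would be 64 seats, not 32. The four periods may be left over from a design in which every group attended classes or demonstrations. This is fair, but it favours the one-class reading, which is the worse one.

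The mixed model's random effects are unspecified, so it could carry a class term. None is named, however, and the ANOVAs name none either.

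Finally, this is a pilot with no power calculation, and the plan does not say that the A-versus-B contrast itself will size the next study. If only an SD is carried forward, the loss is small: at ICC 0.05 the within-class SD is √0.95 = 0.975 of the total, about 2.5% low, or about 5% in n. That also stands. The harm arises if the observed A-versus-B effect or its interval is carried forward, or if the larger study repeats class-level allocation without a design effect.

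**Conclusion.** The concern holds. Follow-up support in the class arms is allocated by class period, membership is by availability, and no planned analysis accounts for class. The structural conclusion needs no assumed ICC: A versus B rests on one class per arm (complete aliasing) or on two (at most 2 df). The size of the type I error inflation does depend on the ICC. Over 0.02 to 0.10, a nominal 5% student-level test at one time point runs at about 9% to 23% with one class per arm and 7% to 14% with two. Pooling with the controls reduces this, and change scores remove it if class effects are stable. The wording about randomising 64 students makes matters worse, because it invites readers to take A versus B as individually randomised. For a pilot this should be fixed; it does not invalidate the trial.

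**What to change.** Phase 2 was due to start in mid-January 2020 and the document carries an approval stamp of 4/14/2020, so allocation has probably already happened. In that case:

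1. State the number and size of classes per arm, and reconcile the opening summary and Study Design with Procedures on the unit of allocation.
2. Report A versus B descriptively, as a one- or two-cluster comparison, focused on change from the end of Phase 1.
3. Do not size the larger study from A versus B as if students were independent.
4. Report C versus D as the randomised estimate of support in students without classes, and say that it does not answer whether support maintains class gains.

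The cost is a class identifier in the dataset and a few sentences in Procedures, Statistical Considerations and Sample Size. No new data are needed, but A versus B can no longer be read as a test of support.

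If allocation is still open, and in the larger study: randomise individuals to follow-up or none within each class period, after the Phase 1 assessment and before Phase 2. Announce the result only then, in the control arm too, and include class period as a stratification factor in the Aim 2 ANOVA and mixed model. This needs a new random list but no extra kits, staff or participants.

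The downside is sharing between classmates, who cook in pairs and whose kits serve two. The documents give no rate. If 10% or 20% of the contrast were lost, the required n would rise by 1/0.9² = 1.23 or 1/0.8² = 1.56 times. At 20% the detectable difference is 1.00 / 0.8 = 1.25 SD, still well below the 2.3 SD of a class-level test with two classes per arm.
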